5.1.2.2. Lupus Nephritis

A main complication of systemic lupus erythematosus (SLE) is nephritis, also known as lupus nephritis, which is classified as a secondary form of glomerulonephritis. Up to 60% of adults with SLE have some form of kidney involvement later in the course of the disease [Koda-Kimble 2012] with a prevalence of 20-70 per 100,000 people in the US. Lupus nephritis often presents in patients with other symptoms of active SLE, including fatigue, fever, rash, arthritis, serositis, or central nervous system disease [Pisetsky 1997]. Some patients have asymptomatic lupus nephritis; however, during regular follow-up, laboratory abnormalities such as elevated serum creatinine levels, low albumin levels, or urinary protein or sediment suggest active lupus nephritis.

Autoimmunity plays a major role in the pathogenesis of lupus nephritis. These autoantibodies form pathogenic immune complexes intravascularly, which are deposited in glomeruli. Autoantibodies may also bind to antigens already located in the glomerular basement membrane, forming immune complexes *in situ*. Immune complexes promote an inflammatory response by activating complement and attracting inflammatory cells [D'Agati 2007]. Thus, immune complex-mediated complement activation plays a key role in the pathogenesis of lupus nephritis. C4d deposits are present in renal tissue and are usually associated with immune complex deposits, C1q, and C3, invoking the classical pathway. In some cases C4d deposits are present without C1q, indicating possible lectin pathway involvement [Kim 2013]. In further support of an important contribution for the lectin pathway, deposits of MBL occur in skin lesions of SLE patients [Wallim 2014]. Additionally, robust deposition of MBL and ficolins in the majority of renal biopsies from patients with lupus nephritis has been observed [Nisihara 2013]. Renal MBL deposition was most evident in patients with high proteinuria. Furthermore, plasma MBL levels were significantly higher in SLE patients than in healthy controls and MBL levels correlated with disease activity, suggesting that MBL levels may represent a biomarker for SLE disease activity [Panda 2012].

CONFIDENTIAL

No use, disclosure or reproduction outside of Omeros without prior written authorization

Corticosteroids are the major conventional treatment option for patients with mild lupus nephritis. For more severe cases, high-dose prednisone, methylprednisolone, mycophenolate mofetil, cyclophosphamide, azathioprine, and cyclosporine have been used in clinical practice. Treatment options for SLE and lupus nephritis have high associated morbidity and mortality. Side effects, particularly from long-term corticosteroid usage, limit patient adherence with subsequent impact on treatment efficacy. There is a need to develop better tolerated treatment regimens.

5.1.2.3. Primary Membranous Nephropathy

Membranous nephropathy (MN) has an estimated incidence in the Western world at 1.2 per 100,000 persons/year [McGrogan 2011]. Initial manifestations of the disease are related to the nephrotic syndrome: proteinuria, hypoalbuminemia, hyperlipidemia, and edema. Membranous nephropathy is more likely than other causes of the nephrotic syndrome to lead to venous thromboembolic events such as deep vein or renal vein thrombosis, and pulmonary embolism [Kerlin 2012].

Membranous nephropathy is an immune-mediated glomerular disease and one of the most common causes of the nephrotic syndrome in adults. The disease is characterized by the formation of immune deposits on the outer aspect of the glomerular basement membrane, which contain podocyte antigens and antibodies specific to those antigens, resulting in complement activation. On immunofluorescence staining, IgG is nearly always accompanied by C3 in a fine granular pattern demonstrating complement activation. The observed IgG is IgG4, which does not activate the classical pathway of complement. This suggests that the classical pathway is not activated. In over 90% of patients with primary MN anti-PLA2R antibody is detected on biopsy [Qin 2011]. These autoantibodies are associated with clinically active disease, and decline or disappear with spontaneous or treatment-induced remission. However, evidence indicates that IgG4 anti-PLA2R autoantibodies can bind mannan-binding lectin and, thus, may activate complement via the lectin pathway [Ma 2013]. The mechanism by which the lectin pathway might be activated in MN is incompletely understood. The N-linked carbohydrate moieties on autoreactive IgG4 in MN patients may be hypogalactosylated, resulting in exposure of terminal GlcNAc residues, allowing MBL to bind and thereby activate complement by the lectin pathway [Beck 2010, Ma 2011, Salant 2013].

Although MN may spontaneously remit without treatment, as many as one third of patients have progressive loss of kidney function and may progress to ESRD at a median of 5 years after diagnosis. Often, corticosteroids are used to treat MN and there is a need to develop alternate therapies. Additionally, patients determined to be at moderate to high risk for progression, based on severity of proteinuria, are treated with prednisone in conjunction with cyclophosphamide or a calcineurin inhibitor, and these two treatments together are often associated with severe systemic adverse effects.

5.1.2.4. C3 glomerulopathy including dense deposit disease

Complement component 3 (C3) glomerulopathies have glomerular deposits made solely of C3 and no immunoglobulin. They are caused by dysregulation of the AP through inherited or acquired defects. The prevalence is approximately 1 – 2 cases per million [Medjeral-Thomas 2014]. The clinical presentation often includes persistent microscopic hematuria with or without

[figure not shown]
episodes of macroscopic hematuria [Bennett 1989]. Invariably there is progression of disease and in one study with a median follow-up of 28 months, 29% of patients had developed ESRD [Medjeral-Thomas 2014].

It is thought that C3 glomerulopathy may share genetic risk factors with atypical hemolytic uremic syndrome (aHUS) [Servais 2012], suggesting commonalities in pathogenesis. One striking observation in patients with C3 glomerulopathy is that the clinical presentation is often preceded by an infectious episode. This suggests that the infectious episode may trigger the initial complement activation, which is then amplified uncontrollably due to AP dysregulation to induce manifestations of C3 glomerulopathy in predisposed individuals.

Treatment is not well described and corticosteroids may be used. There are case reports on treatment with eculizumab, a complement factor 5 inhibitor [Bomback 2012, Herlitz 2012]. Few therapies are available and there is a medical need for therapies that work at the level of C3.

5.2. Previous Experience

5.2.1. Nonclinical Experience

CONFIDENTIAL

No use, disclosure or reproduction outside of Omeros without prior written authorization

5.2.2. Clinical Experience

5.3. Potential Risk and Benefits

5.3.1. Known and Potential Risks

5.3.1.1. Human MASP-2 Deficiency

MASP-2 deficiency has been reported to occur in humans and the clinical phenotype of MASP-2 deficiency may be relevant to risk assessment of MASP-2 inhibition with OMS721. The literature contains conflicting reports as to whether subjects with MASP-2 deficiency are at risk for adverse effects.

Two case reports described individuals with MASP-2 deficiency due to a homozygous mutation (D120G) with clinical associations with autoimmunity or recurrent bacterial infections; one

CONFIDENTIAL

No use, disclosure or reproduction outside of Omeros without prior written authorization

patient was healthy until 13 years of age and the other patient had cystic fibrosis [Olesen 2006, Stengaard-Pedersen 2003]. A genetic screen of 335 Polish children with recurrent respiratory tract infections identified one child with MASP-2 deficiency [Cedzynski 2004]. In contrast, in a genetic screen of 868 healthy Spaniards, two homozygous D120G individuals were identified; both subjects were healthy without clinical evidence of recurrent infections or autoimmune disorders and both had normal levels of circulating complement [Garcia-Laorden 2006].

The gene frequency of the D120G mutation is 2-4% in European populations, which would predict that approximately 1 in 625 to 2000 individuals in this population would be homozygotes with MASP-2 deficiency [Garcia-Laorden 2006, Thiel 2007]. Polymorphisms in the MASP-2 gene as well as the plasma concentration of MASP-2 are influenced by race. For example, the D120G mutation is the most common one in Caucasians, but it is not found in Chinese or Africans [Thiel 2007]. Moreover, the circulating levels of MASP-2 were lowest in Africans (median 196 ng/mL), followed by Chinese (262 ng/mL), and Amerindian (290 ng/mL), and highest in Caucasian Danes (416 ng/mL) [Thiel 2007]. The initial studies were in Danes and a plasma concentration below 100 ng/mL was suggested as indicating MASP-2 deficiency since only individuals homozygous for the D120G mutation had this level. Subsequent studies in broader populations showed that this cutoff was inappropriate since 5% of Chinese and 19% of Africans tested had values below 100 ng/mL.

[figure not shown]
Several studies have examined the relationship between MASP-2 concentration and susceptibility to infections. In a Swiss study of 94 pediatric cancer patients, MASP-2 deficiency defined as serum levels below 200 ng/mL was identified in nine children [Schlapbach 2007]. Patients with low MASP-2 levels had significantly more episodes of febrile neutropenia with no identified microbial etiology and had longer duration of IV antibacterial therapy than those with normal MASP-2 levels. In a Polish study of 1788 neonates, cord blood serum MASP-2 concentration correlated with gestational age and birth weight and was significantly lower in premature babies and other pre-term babies compared with term babies [St Swierzko 2009]. Neonates with low MASP-2 concentrations did not have a higher incidence of perinatal infections when compared with those with normal MASP-2. Indeed, there was a trend towards higher MASP-2 concentrations among babies with infections. A study in Spain evaluated the frequency of D120G mutation in 868 healthy subjects as well as 967 adult patients with community-acquired pneumonia, 43 children with recurrent respiratory infections, and 130 patients with SLE and found that the allelic frequency of the D120G mutation was similar in all of these clinical groups [Garcia-Laorden 2006]. These investigators conducted a follow-up study in which they evaluated the significance of MASP-2 deficiency in the susceptibility and outcome of community-acquired pneumonia in adults and found similar MASP-2 alleles and genotypes among patients and control subjects, leading to the conclusion that MASP-2 deficiency was not associated with an increased risk of community-acquired pneumonias [Garcia-Laorden 2008].

In summary, the literature does not provide a clear indication as to the risk for increased susceptibility to infections in individuals with MASP-2 deficiency. The researchers in Denmark who were the first to describe MASP-2 deficiency and have done the most work in this area stated in one article [Thiel 2007] that “One must conclude that (MASP-2) deficiency in itself does not result in disease, rather, it is a modifier, which may penetrate when also other elements are compromised.”

[figure not shown]

5.3.2. Potential Benefits

5.3.3. Risk – Benefit Summary

6. STUDY PURPOSE AND OBJECTIVES

The purpose of this Phase 2 study is to evaluate the safety, efficacy, pharmacokinetics (PK), and pharmacodynamics (PD) of OMS721 in subjects with glomerulonephropathies. Three cohorts will be evaluated: one cohort who is corticosteroid-dependent and two cohorts that are not receiving corticosteroids.

6.1. Primary Objective(s)

The primary objective of this study is to describe the safety and tolerability of OMS721 administered to subjects with IgAN, lupus nephritis, MN, or C3 glomerulopathy, including dense deposit disease, as assessed by adverse events (AEs), vital signs, clinical laboratory tests, and electrocardiograms (ECGs).

6.2. Secondary Objective(s)

The secondary objectives of this study are to describe the effect of OMS721 administered to subjects with IgAN, lupus nephritis, MN, or C3 glomerulopathy including dense deposit disease on:

- Proteinuria assessed by 24-hour urine protein excretion by disease
- Urine albumin/creatinine ratio by disease
- Corticosteroid dose needed to maintain stable renal function by disease (Cohort 1)
- PK
- PD

6.3. Exploratory Objectives

The exploratory objectives of this study are to describe the effect of OMS721 administered to subjects with IgAN, lupus nephritis, MN, or C3 glomerulopathy including dense deposit disease on:

- Serum creatinine by disease
- Estimated glomerular filtration rate (eGFR) by disease state calculated by the Modification of Diet in Renal Disease (MDRD) equation, the Chronic Kidney Disease Epidemiology Collaboration (CKD-EPI) equation using serum creatinine, the CKD-EPI equation using cystatin C, and the CKD-EPI equation using creatinine – cystatin C
- Urine protein/creatinine ratio by disease
- Occurrence of anti-drug antibodies (ADA) and neutralizing antibodies (NAb)
- Urine inflammatory markers by disease
- Duration of therapeutic response, if observed, defined as the number of consecutive weeks that 24-hour urine protein < 50% of baseline for up to 104 weeks (Cohort 3 only)

7. STUDY DESIGN AND PROCEDURES

7.1. Summary of Study Design

This is a Phase 2, multicenter study of OMS721 in subjects with the following diseases: IgAN, lupus nephritis, MN, or C3 glomerulopathy including dense deposit disease. Three cohorts will be enrolled:

- Cohort 1 will be subjects with corticosteroid-dependent IgAN, LN, MN, or C3 glomerulopathy. All Cohort 1 subjects will be receiving a corticosteroid dose of ≥ 10 mg of prednisone or equivalent dose for at least 12 weeks. Cohort 1 subjects will all receive OMS721 4 mg/kg intravenously (IV) once weekly for 12 weeks.
- Cohort 2 will be subjects with IgA nephropathy who are not receiving corticosteroids. Cohort 2 subjects will receive either OMS721 4 mg/kg IV treatment or 5% dextrose in water (D5W) vehicle once weekly for 12 weeks in a randomized double blind design.
- Cohort 3 will be subjects with IgA nephropathy who are not receiving corticosteroids. Subjects in Cohort 3 will receive either OMS721 370 mg IV or 5% dextrose in water (D5W) vehicle in a randomized double blind design. Regardless of treatment assignment, subjects in Cohort 3 will be eligible for additional open-label OMS721 treatment if they fail to achieve a 24-hour urine protein $< 50\%$ of baseline or their 24-hr urine protein is $> 1000\text{mg}/24\text{-hours}$ after 12 weeks of dosing [plus a 6-week follow-up period].

Cohorts 1 and 2 are ongoing at the time of this amendment. Upon approval of this amendment, subjects with IgAN in Cohort 1 and subjects in Cohort 2 who have started study drug and are on study will be offered the opportunity to roll into Cohort 3 for extended treatment and long-term follow-up. Subjects have to sign an informed consent and meet the eligibility criteria in order to participate in Cohort 3. The rollover subjects will not be randomized and will receive open-label OMS721 370 mg IV once per week for the remaining treatment period of their original cohort. Following rollover they will follow all study procedures for Cohort 3. Subjects with IgAN in Cohort 1 must have discontinued corticosteroids in order to roll into Cohort 3. Subjects with LN, MN or C3 glomerulopathy in Cohort 1 are not eligible rollover into Cohort 3.

Approximately 44 subjects will be enrolled (16 in Cohort 1, 10 in Cohort 2, and 18 in Cohort 3) from up to approximately 15 investigative sites.

For all subjects in Cohort 1 and Cohort 2, the study will consist of screening (4 weeks), treatment (12 weeks), and follow-up (6 weeks) periods.

For subjects in Cohort 3, the study will consist of screening (4 weeks), initial treatment (12 weeks) and initial follow-up (6 weeks). Cohort 3 subjects who have 24-hour urine protein $\geq 50\%$ of baseline or $> 1000\text{ mg}/24\text{ hours}$ at the end of the initial follow-up period (6-week follow-up visit) may elect to receive open-label OMS721 370 mg IV once weekly for 12 additional weeks. Follow-up for all Cohort 3 subjects will be 104 weeks from the first dose of study drug.

Subjects will have two screening visits within a 28-day screening period. Within the screening period and before the first study drug dose, consented subjects will provide three urine samples

CONFIDENTIAL

No use, disclosure or reproduction outside of Omeros without prior written authorization

(collected once daily) on each of two three-consecutive-day periods to establish baseline values of the albumin/creatinine ratio and protein/creatinine ratio. In addition, the subjects will provide one 24-hour urine protein sample to establish baseline values and confirm eligibility.

During the initial 4 weeks of treatment, Cohort 1 subjects will be maintained on their stable pre-study dose of corticosteroids. This initial 4-week treatment period will allow assessment of whether OMS721 can improve measures of renal function when administered to subjects with steroid-dependent disease when co-administered with corticosteroids. Investigators will be instructed to maintain subjects' dose of corticosteroids during the initial 4-week period unless an increase in corticosteroid dose is medically indicated.

At the end of the initial 4-week treatment period, Cohort 1 subjects will undergo corticosteroid taper over 4 weeks. The target will be a taper to ≤ 6 mg prednisone (or equivalent dose) daily. The taper schedule will be at the discretion of the Investigator. Over this period, the taper will be discontinued in subjects who have deterioration of renal function, as determined by the Investigator. Subjects will be treated with OMS721 through the corticosteroid taper and complete 12 weeks of treatment. The taper of steroids and OMS721 treatment will permit assessment of whether OMS721 allows a decrease in the dose of corticosteroid required to maintain stable renal function.

[figure not shown]
Subjects in Cohort 1 and Cohort 2 will remain in the study for 6 weeks following their last study drug dose. Subjects in Cohort 3 will remain in the study for 104 weeks following their first blinded study drug dose.

Clinic visits for subjects in Cohort 1 and Cohort 2 will occur at screening, weekly through the treatment period, and 1, 4, and 6 weeks following the last dose of study drug. Cohort 1 and Cohort 2 subjects will be in the study for approximately 22 weeks.

Clinic visits for subjects in Cohort 3 will occur at screening, weekly through the treatment period and 1, 4, and 6 weeks following the 12th blinded study drug dose at Week 12. Cohort 3 subjects who have 24-hour urine protein < 500 mg will enter the follow-up period with visits at weeks 26, 39, 52, 65, 78, 91 and 104. Cohort 3 subjects who have 24-hour urine protein > 1000 mg or 24-hour urine protein $\geq 50\%$ of baseline anytime between weeks 18-91 during the follow-up period may elect, with the agreement of the investigator, to receive open-label OMS721 370 mg IV once weekly for 12 weeks. Additional 12-week OMS721 treatment courses may be administered as often as subjects have 24-hour urine protein > 1000 mg or 24-hour urine protein $\geq 50\%$ of baseline during weeks 18-91. Subjects in Cohort 3 will be in the study approximately 25 months.

In Cohort 3, data analyses will be performed after the 6-week follow-up period of the initial 12 weeks of study drug treatment for both the exclusive Asian and non-exclusive Asian groups.

Clinical and laboratory assessments will be done at each study visit as shown in [Figure 1](#).

Figure 1: Study Design Schematic

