Cohort 3 is being added to ensure that all subjects may receive active therapy if they have significant proteinuria following treatment with blinded study drug. Also, because continued suppression of urinary protein has been observed in IgAN subjects treated with OMS721, subjects in Cohort 3 will undergo extended follow-up to determine the duration of the urine protein suppression. Subjects may receive open-label OMS721 treatment if they do not achieve a therapeutic response with the initial 12-week blinded study drug treatment course or if their urinary protein increases after achieving a therapeutic response. Chronic toxicology has been completed and supports indefinite dosing. Follow-up through 24 months with visits approximately every 13 weeks will allow assessment of duration of therapeutic response with minimal burden to subjects. Subjects with IgAN in Cohort 1 and subjects in Cohort 2 who have not completed the study may roll into Cohort 3 to be able to receive extended OMS721 treatment.

Asian subjects with IgAN residing in Asia have been added to provide initial evaluation of OMS721 in this population. The literature reports that IgAN in the Asian population may be more severe due to genetic or environmental conditions [Magistrini 2015].

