10.1.10. Follow-Up Visit 2 (Day 120; +/- 3 days)

Six weeks after the last dose of study drug the following procedures and assessments will be performed:

1. Vital signs will be taken including BP, pulse rate, RR, and temperature (after at least 5 minutes of rest).
2. AEs and concomitant medications, including corticosteroid dose (if applicable) will be recorded.
3. Laboratory samples will be collected for:
 - Hematology, chemistry, coagulation, cystatin C
 - Serum PK samples
 - Serum PD sample
 - Serum ADA sample
4. For three days prior to Follow-Up Visit 2, three once daily first-void urine sample for urine albumin/creatinine and protein/creatinine ratios will be collected and brought in for analysis at this visit.

Subjects in Cohort 1 and Cohort 2 will complete the study at Follow-up Visit 2 provided they have not rolled into Cohort 3.

Subjects in Cohort 3 will undergo extended follow-up with visits at weeks 26, 39, 52, 65, 78, 91 and 104.

10.1.11. Cohort 3 Extended Follow-Up Visits (Weeks 26, 39, 52, 65, 78, 91, and 104; +/- 2 weeks)

At each extended follow-up visit the following procedures will be performed:

1. AEs and concomitant medications will be recorded.

CONFIDENTIAL

No use, disclosure or reproduction outside of Omeros without prior written authorization

2. Laboratory samples will be collected for:
 - Hematology, chemistry, cystatin C
 - Urinalysis
 - Urinary 24-hour protein
 - Urine for inflammatory biomarkers
 - Serum ADA sample
3. Subjects will be provided with supplies to collect 24-hour urine samples in the week prior to next Follow-Up Visit. The investigative site will call the subject one week prior to the next follow-up visit to remind the subject to collect the 24-hour urine sample. Subjects will not be provided with collection supplies at the last Follow-Up Visit.

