Cohort 3 subjects who have 24-hour urine protein > 1000 mg anytime between weeks 18-91 or 24-hour urine protein \geq 50% of baseline during the follow-up period may elect, with the agreement of the Investigator, to receive open-label OMS721 370 mg IV for 12 weeks. Additional 12-week OMS721 treatment courses may be administered as often as subjects have 24-hour urine protein > 1000 mg or 24-hour urine protein \geq 50% of baseline during weeks 18-91. The visit schedule for each series of additional OMS721 treatment is provided below. If a subject receives re-treatment, the subject's re-treatment visit schedule will be followed until the re-treatment follow-up is completed (see below for re-treatment schedule). At that time, the subject's next visit will be at the first regularly scheduled follow-up visit following the initial OMS721 treatment course.

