Clinic visits for subjects in Cohort 1 and Cohort 2 will occur at screening, weekly through the treatment period, and 1, 4, and 6 weeks following the last dose of study drug. Cohort 1 and Cohort 2 subjects will be in the study for approximately 22 weeks.

Clinic visits for subjects in Cohort 3 will occur at screening, weekly through the treatment period and 1, 4, and 6 weeks following the 12th blinded study drug dose at Week 12. Cohort 3 subjects who have 24-hour urine protein < 500 mg will enter the follow-up period with visits at weeks 26, 39, 52, 65, 78, 91 and 104. Cohort 3 subjects who have 24-hour urine protein > 1000 mg or 24-hour urine protein $\geq 50\%$ of baseline anytime between weeks 18-91 during the follow-up period may elect, with the agreement of the Investigator, to receive open-label OMS721 370 mg IV once weekly for 12 weeks. Additional 12-week OMS721 treatment courses may be administered as often as subjects have 24-hour urine protein > 1000 mg or 24-hour urine protein $\geq 50\%$ of baseline during weeks 18-91. Subjects in Cohort 3 will be in the study approximately 25 months.

In Cohort 3, data analyses will be performed after the 6-week follow-up period of the initial 12 weeks of study drug treatment for both the exclusive Asian and non-exclusive Asian groups.

Study visits are shown in Section 5.

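### The 500 mg condition for entering Cohort 3's Week 26–104 follow-up conflicts with the statements that follow every Cohort 3 subject; applied literally, it would leave some responders without visits after Week 18

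*Protocol*

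**What the plan says.** The condition stands in Protocol 7.1: "Cohort 3 subjects who have 24-hour urine protein < 500 mg will enter the follow-up period with visits at weeks 26, 39, 52", with the list running on to Week 104. The synopsis has the same sentence, and so does SAP 4: "Cohort 3 subjects who have 24-hour urine protein < 500 mg will enter the follow-up period".

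Other statements set no threshold:

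- Protocol 7.1, on the study periods: "Follow-up for all Cohort 3 subjects will be 104 weeks from the first dose of study drug".
- Protocol 7.1, on time in study: "Subjects in Cohort 3 will remain in the study for 104 weeks following their first blinded study drug dose". The same section gives about 25 months.
- Protocol 10.1.10: "Subjects in Cohort 3 will undergo extended follow-up with visits at weeks 26, 39, 52, 65, 78, 91 and 104". Section 10.1.11 then lists 24-hour urine protein among the samples at each of these visits.
- Protocol 7.2 gives duration of urine protein suppression as the reason for extended follow-up, for Cohort 3 as a whole.
- The extended follow-up column in Protocol 19.2 and SAP 5.1 is headed for Cohort 3 without qualification.

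Re-treatment has its own rule, stated in 7.1 and again at the end of 10.1.11, which begins: "Cohort 3 subjects who have 24-hour urine protein > 1000 mg anytime between weeks 18-91". It is open at more than 1000 mg or at 50% of baseline or above, and the subject may elect it. Response is a 24-hour urine protein below 50% of baseline (Protocol 7.3.3, SAP 6).

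**The concern.** Three cut-offs meet at Week 18: below 50% of baseline for response, at least 50% of baseline or above 1000 mg for re-treatment, and below 500 mg for the extended visits. If the last is read as an entry rule, the three do not cover every subject.

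Week 18 is also the first scheduled 24-hour collection after baseline (Protocol 19.2, SAP 5.1). A responder whose visits stopped there would contribute one post-baseline value to an endpoint that counts consecutive weeks of response up to Week 104. Protocol 13.2.1.1 uses observed data without imputation, and SAP 12.9 summarises duration descriptively with no censoring rule. If some sites applied the 500 mg sentence and others applied 10.1.10, who is followed would depend on the site and on the subject's own Week 18 result. Values never collected cannot be recovered in analysis. Protocol 13.1 justifies the Cohort 3 sample size partly by the wish to explore duration of response.

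**Working it through.** **The plan's own duration figure.** Screening of 4 weeks plus 104 weeks gives (4 + 104) × 7 / 30.4375 = 24.8 months, which matches the stated 25 months. A subject whose visits ended at Follow-Up Visit 2 (Week 18) would be in the study (4 + 18) × 7 / 30.4375 = 5.1 months. The stated time in study therefore fits follow-up of everyone and does not fit a gate.

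**Where the literal rules leave a hole.** Let B be baseline and U the Week 18 value in mg per 24 hours. Inclusion criterion 5 requires B > 1000, so 0.5B is always above 500.

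- Extended follow-up, read literally: U < 500.
- Re-treatment open: U > 1000 or U ≥ 0.5B.
- Neither: 500 ≤ U ≤ 1000 and U < 0.5B.

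Everyone in the third set is a responder, because U < 0.5B. The set can occur at every eligible baseline:

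| B (mg) | 0.5B (mg) | Neither path (mg) | Re-treatment open (mg) |
|---|---|---|---|
| 1200 | 600 | 500 to < 600 | ≥ 600 |
| 1500 | 750 | 500 to < 750 | ≥ 750 |
| 2000 | 1000 | 500 to < 1000 | ≥ 1000 |
| 3000 | 1500 | 500 to 1000 | > 1000 |

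Example: 2000 to 800 mg is 800 / 2000 = 40% of baseline. That is a response, is not open to re-treatment and is not below 500 mg. By contrast, 1200 to 700 mg is 58% of baseline, so that subject is a non-responder and may be re-treated. Not everyone between 500 and 1000 mg is in the hole.

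A second group follows from re-treatment being elective. Anyone who qualifies has U ≥ 500, so a subject who declines also has no path under the literal sentence.

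**How many responders.** The documents give neither a baseline distribution nor a variance of change, so this part rests on assumptions. Baseline was taken as log-normal with median parameter 1500, 2000 or 3000 mg and log-SD 0.5, truncated to values above 1000 mg. The ratio U/B was taken as log-normal with median 0.3, 0.4, 0.5 or 0.7 and log-SD 0.4 or 0.6. Over these 24 combinations:

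- share of all Cohort 3 subjects in the hole: 6% to 40%, which is 1.1 to 7.2 of 18;
- share of responders in the hole: 32% to 59%.

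A case that can be checked by hand uses one fixed baseline, B = 2000, median ratio 0.5 and log-SD 0.5. The probability of response is Φ(0) = 0.500. The probability of U < 500 is Φ[(ln 0.25 − ln 0.5) / 0.5] = Φ(−1.386) = 0.083. The share of responders in the hole is (0.500 − 0.083) / 0.500 = 83%. At B = 3000 the same assumptions give 39%. The share depends strongly on baseline, so the range over a spread of baselines is the better guide. Subjects who decline re-treatment are not counted in any of these figures.

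**The case against.** The strongest reply is that the sentence is loose summary wording and that the rest of the plan already follows everyone. Much of this stands.

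- The sentence does not say that only subjects below 500 mg enter follow-up, and it tells no site to stop following anyone.
- The next sentence in 7.1 speaks of subjects above 1000 mg, or at 50% of baseline or more, as being in the follow-up period.
- SAP 5.1, footnote 1, has urine collection supplies dispensed at Follow-Up Visit 2 to any subject not going into re-treatment. That covers both the 800 mg responder and the subject who declines.
- Protocol 8.3.2 has no withdrawal rule based on proteinuria, and the SAP visit windows (Table 2) carry no threshold.

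A reader might therefore infer that moderate responders are excluded and their duration of response is lost. The documents do not support that as a fact; the loss needs a site to use the sentence as a gate against the procedures section. What the reply does not explain is what the condition is for. It appears in three places across two documents, and it has no function if everyone enters follow-up.

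A reader might also see a second contradiction: 7.2 describes open-label drug for subjects "if they do not achieve a therapeutic response with the initial 12-week blinded study drug treatment course or if their urinary protein increases" after a response, yet a fall from 3000 to 1200 mg (40% of baseline) is a response that still qualifies through the 1000 mg limb. This is weak. The same paragraph of 7.2 opens by giving significant proteinuria after blinded treatment as a ground for active therapy.

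Finally, duration of response is exploratory, and the trial is descriptive with safety as its primary endpoint. That limits the weight of the point.

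**Conclusion.** The inconsistency is real and should be fixed, but it is not a defect that by itself invalidates the trial. The 500 mg condition cannot be squared with the statements that follow all Cohort 3 subjects to Week 104, and the plan's own 25 months agrees with the latter. The harm is conditional on a site applying the sentence as a gate. In that case the subjects cut off would be selected by their outcome. The direction of the bias cannot be stated in advance, because it depends on whether a responder last seen at Week 18 is given a short duration or left out.

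The existence of the hole follows from the documents alone. The figure of about 1 to 7 of 18 subjects, or roughly one-third to three-fifths of responders, rests entirely on the assumed distributions and is illustrative.

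**What to change.** Remove the below-500 mg condition on entry to extended follow-up from the synopsis, Protocol 7.1 and SAP 4, so that they agree with the all-subject statements in 7.1 and with 10.1.10. Every Cohort 3 subject is then on the Week 26–104 schedule, with the exception that 10.1.11 already makes: re-treated subjects follow the re-treatment schedule through its follow-up visit and resume at the next regular visit. For example, a course starting at Week 18 has its follow-up visit at about Week 18 + 12 = 30, so the Week 26 visit is replaced and the subject resumes at Week 39. The replacement sentence should not ask for all regular collections during a re-treatment course, since that would create a new conflict.

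This changes who has follow-up data collected and leaves the re-treatment criteria untouched. If the sponsor sees a difference between those criteria and the rationale in 7.2 for responders still above 1000 mg, the sponsor should reconcile the passages. No additional SAP breakdown by re-treatment eligibility is needed; SAP 12.4 plans no subgroups, and about 18 subjects would not support one.

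The cost is one sentence in each of three places. It adds no visits beyond those that 10.1.10 and the schedules already require.
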